7.14 Investigational Product Retention at Study Site

At the conclusion of the study, and as appropriate during the course of the study, with instruction from the sponsor, the designated study personnel will destroy test article on site as permitted by local site operating procedures, or return all unused test articles, packaging, and drug labels. Destruction/return of all test article will be documented and maintained in the site files.

8 STUDY PROCEDURES

Written, signed, and dated informed consent will be obtained by subject's parent/LAR before any study-related procedures have been performed. Pediatric assent is also required as appropriate per local regulations. Upon signing of the informed consent and pediatric assent, the subject will then be assigned a study subject number. Adverse events (AEs) must be recorded from the time the ICF/pediatric assent is signed. The investigator will maintain a subject master list to document every subject who has signed an ICF/pediatric assent. A copy of this list should be retained in the investigator's study files.

8.1 Informed Consent and Pediatric Assent

The investigator will provide for the protection of the subjects by following all applicable regulations. These regulations are available upon request from the sponsor. The ICF and pediatric assent must be reviewed by the sponsor and approved by the IRB/IEC/REB.

Before any procedures specified in the protocol are performed, a subject and his/her parent/LAR must:

- Be informed of all pertinent aspects of the study and all elements of informed consent and pediatric assent (when applicable)
- Be given time to ask questions and time to consider the decision to participate
- Voluntarily agree to participate in the study
- Sign and date an IRB/IEC/REB approved ICF and pediatric assent (when applicable)

8.2 Subject Demographics/Other Baseline Characteristics

Subject demographic and Baseline characteristic data to be collected at screening on all subjects include date of birth, gender, and race/ethnicity.

8.3 Medical History

The investigator will perform a comprehensive history at the Screening visit. Significant medical history (at any time) and any medical history within the past 6 months including ongoing medical conditions at the time of signing of the ICF/assent will be recorded.

Where possible, diagnoses are to be recorded. Any event or change in the subject's condition or health status occurring after signing the ICF will be reported as an AE.

8.4 Physical Examination

At Screening, a full physical examination will include the examination of general appearance, skin, neck, eyes, ears, nose, throat, lungs, heart, abdomen, lymph nodes, extremities, and brief neurological exam.

Information for all physical examinations must be included in the source documentation at the study site. Significant and relevant findings that are present prior to the start of test

article must be included in the subject's eCRF. Relevant findings that are present prior to the start of test article must be included in the relevant medical history/current medical conditions screen on the subject's eCRF. Significant findings made after the start of test article which meet the definition of an AE must be recorded on the AE screen of the subject's eCRF.

8.5 Vital Signs

Vital signs (blood pressure [BP], heart rate [HR], and body temperature) will be measured at the timepoints indicated in the Schedule of Events ([Appendix 1](#)).

The subject's BP and heart rate at all time points should be captured after at least 5 minutes (+ 5 minutes) of rest while in a supine position.

Systolic and diastolic BP will be measured using an automated calibrated device, with an appropriately sized cuff. Heart rate will be measured using an automated calibrated device, when available. If not available, heart rate will be measured manually.

Temperature will be obtained using an electronic (rapid reading) device whenever possible. Temperature can be measured using the method preferred by the study site (e.g., oral, rectal, tympanic membrane, axillary). Both the temperature and method of measurement will be captured in the eCRF.

8.6 Height, Weight, and BMI

Both height and body weight will be obtained with shoes off.

8.7 Clinical Laboratory Tests

All laboratory testing will be performed by the local laboratory at each site. All hematology and serum chemistry parameters and blood tests outlined in Table 1 and Table 2 are required to be collected to determine study eligibility. Laboratory tests collected as part of standard of care within 24 hours of consent/assent may be used for determining eligibility and do not need to be repeated provided that all protocol required parameters have been collected.

If any of the required parameters are not collected as part of standard of care testing, laboratory samples must be drawn and results obtained for missing parameters in order to determine subject eligibility.

The relevant local laboratory results from Screening will be used to assess eligibility as per the inclusion/exclusion criteria.

8.7.1 Hematology and Serum Chemistry

Blood testing will include the hematology and serum chemistry parameters as shown in [Table 1](#) and [Table 2](#), respectively. These results for the study timepoints indicated in [Appendix 1](#) will be recorded in the eCRF.

Table 1 Hematology

Hematocrit	White blood cell differential (as % cell counts)
Hemoglobin	Neutrophils
Mean cell volume	Lymphocytes
WBC count	Monocytes
Platelet count	Eosinophils
	Basophils

WBC = white blood cell

Table 2 Serum Chemistry

Blood glucose	ALT	CK
Urea	AST	Calcium
Creatinine	AP	Phosphate
Sodium	Total bilirubin	Cholesterol
Potassium	Total protein	Uric Acid
Chloride	Albumin	GGT
Bicarbonate		Amylase
		Lipase

ALT = alanine aminotransferase, AP = alkaline phosphatase, AST = aspartate aminotransferase,
CK = creatine phosphokinase, GGT = gamma-glutamyl transpeptidase

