6.2 Inclusion and Exclusion Criteria

Each subject must meet all of the following criteria at Screening and/or Pre-dose to be eligible to participate in the study:

Main Criteria for Inclusion:

1. Written and signed parental/LAR informed consent must be obtained before any protocol specific assessment is performed. Pediatric assent should be obtained in accordance with local hospital and IRB policies.
2. Male and female subjects between 8 and < 18 years of age, inclusive at time of consent/assent.
3. Hospitalized, in stable condition, likely to survive the current illness, and receiving or planned to receive standard of care systemic antibacterial therapy, other than omadacycline, for a suspected or confirmed bacterial infection.
4. Expected to remain hospitalized for at least 2 days following administration of the study drug.
5. Sufficient intravascular access (peripheral or central) for study drug administration (iv treatment only) and blood draws.
6. For subjects who will receive oral study drug only, ability to swallow oral study drug (2 tablets).
7. Weight within the 5th and 95th percentile for age and sex.
8. Females of reproductive potential (post-menarche or has reached Tanner Stage 3 breast development) must have a negative urine or serum pregnancy test and agree to use a highly effective form of birth control (e.g., abstinence, oral contraceptive, intrauterine device, or barrier contraception [e.g., condom]) from Screening through the study completion visit. Males (if sexually active) must agree to use a highly effective method of birth control with female partner(s).
9. Subject and parent/caregiver is willing and able to adhere with the requirements and restrictions of the study.

Main Criteria for Exclusion:

Subjects meeting any of the following criteria at Screening and/or Pre-dose will be excluded from participation in the study:

1. Use of other investigational drugs within 5 half-lives or 30 days prior to Pre-dose, whichever is longer.
2. Evidence or history of a clinically significant medical condition or planned medical intervention that may, in the opinion of the investigator, pose a significant safety risk, impair study participation, or impact the subject's ability to undergo the required study procedures. (Note: Subjects must, in the opinion of the investigator, be physically and mentally competent to participate.)

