12.10 Multiple Comparisons and Multiplicity

No formal comparisons are planned.

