13.8 Pre-Study Documentation

The investigator must provide the sponsor with the following documents before enrolling any subjects:

- Completed and signed form 1572 or equivalent
- All applicable country-specific regulatory forms
- Current signed and dated curricula vitae for the investigator, sub-investigators, and other individuals having significant investigator responsibility who are listed on the form 1572 or equivalent, or the clinical study information form
- Copy of the IRB/IEC/REB approval letter for the protocol and informed consent and pediatric assent. All advertising, recruitment, and other written information provided to the subject must be approved by the IRB/IEC/REB. Written assurance of continuing approval (at least annually) as well as a copy of the annual progress report submitted to the IRB/IEC/REB must also be provided to the sponsor.
- Copy of the IRB/IEC/REB-approved informed consent and pediatric assent documents to be used
- Where applicable, a list of the IRB/IEC/REB members and their qualifications, and a description of the committee's working procedure
- Copy of the protocol sign-off page signed by the investigator
- Fully executed CSA
- Where applicable, a financial disclosure form
- A written document containing the name, location, certification number, and date of certification of the laboratories to be used for laboratory assays and those of other facilities conducting tests. This document should be returned along with the statement of investigator form. The sponsor must be notified if the laboratory is changed or if any additional laboratory is to be used.
- List of normal laboratory values and units of measure for all laboratory tests required by the protocol. This is required for each laboratory to be used during the study. The sponsor must be notified if normal values or units of measurement change.

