9.2 Clinical Laboratory Tests

All laboratory testing will be performed by the local laboratory at each site. The relevant local laboratory results from Screening will be used to assess eligibility as per the inclusion/exclusion criteria.

The following laboratory tests will be performed:

Hematology	Hematocrit, Hemoglobin, Mean cell volume, WBC count, Platelet count, White blood cell differential, Neutrophils, Lymphocytes, Monocytes, Eosinophils, Basophils
Serum Chemistry	Blood glucose, Urea, Creatinine, Sodium, Potassium, Chloride, Bicarbonate, ALT, AST, AP, Total bilirubin, Total protein, Albumin, CK, Calcium, Phosphate, Cholesterol, Uric Acid, GGT, Amylase, Lipase

SARS-CoV-2 Sample	Molecular testing for SARS-CoV-2 will be performed at the local laboratory using an upper respiratory sample (e.g. nasopharyngeal swab or saliva) collected either at Screening or upon current hospital admission. Test results from this sample are not required before a subject is enrolled
Pregnancy Assessment	Females of reproductive potential (post-menarchal or has reached Tanner Stage 3 breast development) will have a local laboratory urine or serum pregnancy test at Screening.

ALT = alanine aminotransferase, AP = alkaline phosphatase, AST = aspartate aminotransferase, CK = creatine phosphokinase, GGT = gamma-glutamyl transpeptidase

The hematology, Serum Chemistry, SARS-CoV-2 sample, and pregnancy assessment tests will be performed at the timepoints indicated in the schedule of events (SOE). The schedule of events can be found in [Section 11](#).

Clinical laboratory test results will be presented in data listings. Actual results and changes from Baseline in clinical hematology and serum chemistry will be summarized by treatment within each cohort ,and time point. Shift from baseline in terms of low/normal/high for hematology and serum chemistry tests, and in terms of normal/abnormal will be summarized by treatment within each cohort and time point.for the safety population.

All laboratory data will be presented in data listings.

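### The SAP does not put the white-cell differential, collected as percentages, on an absolute-count scale, so its change and shift tables can misstate what a cell type did

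*Protocol*

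**What the plan says.** Protocol 8.7.1, Table 1, gives the unit of the differential: "White blood cell differential (as % cell counts". Neutrophils, lymphocytes, monocytes, eosinophils and basophils come under it. WBC count is a separate entry, and no absolute differential count is listed.

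SAP 9.2 repeats the analytes without a unit: "WBC count, Platelet count, White blood cell differential, Neutrophils, Lymphocytes, Monocytes, Eosinophils, Basophils". It then plans two summaries that cover all hematology:

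- "Actual results and changes from Baseline in clinical hematology and serum chemistry will be summarized by treatment within each cohort"
- "Shift from baseline in terms of low/normal/high for hematology and serum chemistry tests"

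There is no exception for the differential and no derivation of absolute counts.

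Three other passages bear on the point:

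- **Laboratories.** Protocol 8.7: "All laboratory testing will be performed by the local laboratory at each site".
- **Population.** Protocol 6.2 admits hospitalized subjects "receiving or planned to receive standard of care systemic antibacterial therapy, other than omadacycline, for a suspected or confirmed bacterial infection".
- **Timing.** The Schedule of Assessments places hematology at Screening and at 24 hours post-dose only, so each subject contributes one scheduled change.

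**The concern.** The five percentages are parts of a total fixed at 100, so a change in one reflects what the others did as well as what the named cell type did. That matters when total WBC is moving, which is to be expected in children under treatment for bacterial infection.

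The interval can be long enough for a real movement. Screening may begin 48 hours before dosing, standard-of-care results from up to 24 hours before consent may be used, and the post-dose sample is at 24 hours. Baseline to post-dose can therefore span about 24 + 48 + 24 = 96 hours.

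Two kinds of misreading follow. A table can show a rise in lymphocytes, monocytes or eosinophils when the count has not changed or has fallen. And a subject with a low absolute neutrophil count can sit in the normal category of the neutrophil shift table because the percentage is unremarkable. Every subject receives omadacycline, so there is no untreated group against which a reader could recognize the first pattern as a product of the scale.

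**Working it through.** The documents give no figure on this point, so there is none to reproduce. They also give no cell counts and no reference limits. All counts (10^9/L) and limits below are assumptions chosen to show the arithmetic.

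**Formulas.** Let c be the count of one cell type and W the total WBC.

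- Percentage: p = 100 × c / W
- Ratio of percentages, after to before: (c after / c before) ÷ (W after / W before)

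A percentage therefore rises exactly when the count falls proportionally less than WBC, whatever the direction of the count itself.

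**Example A: neutrophils and monocytes both fall.** Neutrophils go from 14.4 to 5.0 and monocytes from 1.2 to 0.6. Lymphocytes stay at 2.0, eosinophils at 0.2 and basophils at 0.05.

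- W before = 14.4 + 1.2 + 2.0 + 0.2 + 0.05 = 17.85
- W after = 5.0 + 0.6 + 2.0 + 0.2 + 0.05 = 7.85, a fall of 56%

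| Cell type | Count | Percentage |
|---|---|---|
| Lymphocytes | 2.0 → 2.0 | 2.0/17.85 = 11.2% → 2.0/7.85 = 25.5% |
| Eosinophils | 0.2 → 0.2 | 0.2/17.85 = 1.1% → 0.2/7.85 = 2.5% |
| Monocytes | 1.2 → 0.6 | 1.2/17.85 = 6.7% → 0.6/7.85 = 7.6% |

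Monocytes fall 50%, less than the 56% fall in WBC, so the tabulated change has the wrong sign. Any site whose lower limit for lymphocyte percentage lies above 11.2 and at or below 25.5 would record this subject as leaving the low category with an unchanged count.

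**Example B: only neutrophils fall.** Baseline: neutrophils 12.0, lymphocytes 2.0, monocytes 0.7, eosinophils 0.2, basophils 0.1, so W = 15. The relative rise in every other white-cell percentage is W before / W after − 1.

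| Neutrophils after | WBC after | Relative rise in the other percentages |
|---|---|---|
| 10 | 13 | 15/13 − 1 = 15% |
| 8 | 11 | 15/11 − 1 = 36% |
| 6 | 9 | 15/9 − 1 = 67% |
| 4 | 7 | 15/7 − 1 = 114% |

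On the absolute scale the row with neutrophils at 8 reads −4.0 for neutrophils and 0 for the other four.

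**Example C: the rise is not universal.** From the same baseline, neutrophils go from 12 to 10 and lymphocytes from 2.0 to 1.0, so W goes from 15 to 12. Lymphocytes fall from 13.3% to 8.3%. Neutrophils rise from 80.0% to 83.3% although their count fell.

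**Example D: a low neutrophil count with an unremarkable percentage.** Absolute count = W × p / 100.

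- W = 2.0, p = 55%: 1.1
- W = 3.0, p = 45%: 1.35

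With a lower limit for the percentage of 35 to 45, both would be classed as normal for neutrophils. With a lower limit for WBC of 4.0 to 5.0, both would be flagged low for WBC. For the count to be low with neither flag, both results must be at or above their limits. With WBC limits of 4.0 to 5.0 and percentage limits of 30 to 45, the smallest unflagged count ranges from 4.0 × 0.30 = 1.2 to 5.0 × 0.45 = 2.25. Masking without any flag is therefore confined to values near the limits and depends on each site's ranges.

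**The case against.** Several objections have force.

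- **The scale is inferred.** SAP 9.2 states no unit, so tabulation as percentages is the default reading and not an explicit instruction. This stands. If absolute counts are intended, the SAP still needs to say so.
- **Other lines need not rise.** A reader might infer that a neutrophil fall pushes up every other cell line. Example C shows otherwise, and hemoglobin, hematocrit and platelets are not part of the total at all. The effect holds for another white-cell type only when its count falls proportionally less than WBC.
- **Low neutrophils would not be missed.** A reader might infer that a low count disappears from view. The documents do not support that. WBC is in the same change and shift tables, all laboratory data are listed, Protocol 12.5 provides for sponsor review as each subject completes, and Protocol 8.14.4 has clinically significant laboratory abnormalities recorded as adverse events. What remains is that the neutrophil table can misclassify the subject, and that a low WBC does not say which line is low.
- **Absolute counts cannot always be derived.** A reader might assume that WBC and the differential share a sample. Protocol 8.7 lets parameters missing from standard-of-care testing be drawn separately, and SAP section 4 takes the last non-missing pre-dose value, including repeats and unscheduled results. Multiplying values from different draws could give a wrong count. This stands and limits the fix.
- **The ranges may not be to hand.** Protocol 13.8 asks sites for a "List of normal laboratory values and units of measure for all laboratory tests required by the protocol". The required differential is in percent, so this does not clearly cover absolute-count ranges at about 15 sites.
- **Attribution stays open.** Without an untreated group, absolute neutrophil changes would also reflect resolving infection. True. The fix removes only the distortion due to scale.

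**Conclusion.** The point holds as a minor improvement. On the default reading, five of the ten hematology results will be summarized on a scale where a change can appear with no change in count (lymphocytes 11.2% to 25.5% in Example A) or with the wrong sign (monocytes 6.7% to 7.6% while the count halves). The neutrophil shift table can class a low absolute count as normal, but under the assumed limits total WBC would usually be flagged low.

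The size rests on assumed counts and limits. In Example B the relative distortion runs from 15% to 114% as the assumed neutrophil fall deepens. How many subjects would cross a category cannot be stated without the sites' ranges.

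The reach is limited to descriptive safety tables under the secondary objective, with about 10 subjects per treatment and age cohort. Protocol 12.10 states "No formal comparisons are planned". The PK endpoints and sample size are untouched. WBC and the percentages are both recorded, so absolute counts can be recovered wherever the two come from one draw.

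**What to change.** In SAP 9.2, state that change-from-baseline and low/normal/high shift summaries of the differential use absolute counts:

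- Use laboratory-reported absolute counts where they are available.
- Otherwise derive WBC × % / 100, only when the WBC and the percentage come from the same draw.
- Classify against the local absolute-count ranges.
- Keep the percentages in the listings.

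No extra blood draw or visit is needed. There are two costs. Local laboratories must supply absolute-count reference ranges as well as percentage ranges. Subjects with no reported absolute count and no same-draw WBC and differential, at baseline or at 24 hours, drop out of that summary, so the tables should show how many contribute.

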8.7.2 SARS-CoV-2 Sample

Testing for SARS-CoV-2 will be performed in accordance with site's standard of care and local policy.

8.7.3 Pregnancy Assessment

Females of reproductive potential (post-menarchal or has reached Tanner Stage 3 breast development) will have a local laboratory urine or serum pregnancy test at Screening. Results are required for eligibility, retained in source documents, and will be entered in the eCRF. If a positive urine or serum pregnancy test result is obtained during Screening, the subject is not to be enrolled.

8.8 Pharmacokinetic Assessments

Instructions will be provided to sites with detailed information on sample collection, handling, and shipment requirements. All samples will be given a unique identifier. The exact clock time of dosing, date and time of last food intake, as well as actual sample collection date and time will be entered on the eCRF. A total of 7 blood samples for pharmacokinetic analysis of oral omadacycline and 8 blood samples for iv omadacycline will be collected at specified time points prior to dosing and throughout the 48 hours from time of dosing.

8.8.1 PK Blood Collection and Processing

Blood Collection (plasma):

Blood samples will be collected and analyzed for omadacycline concentration at the following times:

Oral Treatment

- At least 15 minutes prior to administration of oral omadacycline 300 mg and at 1-hour (± 5 minutes), 2 hours (± 5 minutes), 3 hours (± 5 minutes), 8 hours (± 1 hr.), 24 hours (± 1 hr.) and 48 hours (± 1 hr.) after dosing

Intravenous Treatment

- At least 15 minutes prior to infusion of IV omadacycline 100 mg, at 10 minutes (± 5 minutes), 0.5-hour (± 5 minutes), 1-hour (± 5 minutes), 2 hours (± 5 minutes), 8 hours (± 1 hr.), 24 hours (± 1 hr.) and 48 hours (± 1 hr.) after the end of the IV infusion Storing and Shipping of PK Samples

After all PK samples from a single subject have been collected and frozen at -20°C or colder, the primary samples from each time point can be batched together and carefully packaged and shipped frozen at -20°C or colder to the central laboratory designated by the sponsor. Samples are to be shipped with sufficient dry ice to remain frozen during overnight transit.

8.9 Adverse Events

An AE is any untoward, undesired, or unplanned event in the form of signs, symptoms, disease, or laboratory or physiologic observations occurring in a person given a test article or in a clinical study. The event does not need to be causally related to the test article or clinical study. An AE includes, but is not limited to, the following:

- Any clinically significant worsening of a preexisting condition.
- An AE occurring from overdose of a test article, whether accidental or intentional. Overdose is a dose greater than that specified in the protocol.
- An AE occurring from abuse (e.g., use for nonclinical reasons) of a test article.
- An AE that has been associated with the discontinuation of the use of a test article.

